3.5.2 Phase II

3.5.2.1 Primary endpoints in phase II

The primary endpoint in phase II is the proportion of subjects achieving $\geq 35\%$ reduction in spleen volume from baseline by centrally reviewed MRI/CT at the end of week 24 and week 48.

The percent change from baseline at week 24 or week 48 will be calculated by:

$$\% \text{ change} = \frac{\text{week 24 or 48 value} - \text{baseline value}}{\text{baseline value}}$$

35% Reduction at Week 24 or Week 48: A subject (responder) will be considered as having achieved 35% reduction of the spleen volume from baseline to Week 24 or Week 48 if the subject had evaluable baseline and Week 24 or Week 48 spleen volume assessments, the subject did not experience a protocol-defined progression event prior to the Week 24 or Week 48 visit, and the calculated percent change was less than or equal to -35% .

Listing of the data on response variables as assessed by the investigator will be provided. Recalculated response based on raw measurements will be listed additionally and discrepancies will be identified. Based on this approach, investigator's assessment is considered to be validated and will be used for the primary efficacy analysis.

The uniformly minimum variance unbiased estimator (UMVUE) (Jung and Kim, 2004) for patients achieving 35% spleen volume reduction from baseline as measured by MRI/CT with the exact two-sided 95% confidence interval will be provided in phase II.

Let K be the number of stages, and n_k and X_k denote the number of patients accrued and the number of responders (i.e. subjects achieve $\geq 35\%$ spleen volume reduction), respectively, during stage k , $1 \leq k \leq K$. And let $S_k = \sum_{i=1}^k X_i$ denote the cumulative number of responders by stage k .

The $\hat{p}_1 = X_1/n_1$ is an unbiased estimator of the response rate p (i.e. achieving 35% spleen volume reduction), where X_1 and n_1 denote the number of responders and the number patients accrued at stage 1, respectively.

The UMVUE of the response rate (\tilde{p}) is obtained by

$$\tilde{p} = E\{\hat{p}_1 | (m, s)\}$$

In a two-stage design,

$$\tilde{p} = \begin{cases} \frac{s}{n_1} & m = 1 \\ \frac{\sum_{x_1=(a_1+1) \vee (s-n_2)}^{s \wedge (b_1-1)} \binom{n_1-1}{x_1-1} \binom{n_2}{s-x_1}}{\sum_{x_1=(a_1+1) \vee (s-n_2)}^{s \wedge (b_1-1)} \binom{n_1}{x_1} \binom{n_2}{s-x_1}} & m = 2 \end{cases}$$

Where $a \wedge b = \min(a, b)$ and $a \vee b = \max(a, b)$. a_1 and b_1 is the lower and upper boundaries for stage 1. As there is only a lower boundary in the study, the upper boundary b_1 in this case is $b_1 = n_1 + 1$.

Let M denote the stopping stage and let $S = S_M$ denote the total number of responders accumulated up to the stopping stage. The probability mass function of (M, S) in a two-stage design with lower stopping boundaries only is given as

$$f(m, s | p) = \begin{cases} p^s (1-p)^{n_1-s} \binom{n_1}{s} & m = 1, 0 \leq s \leq a_1 \\ p^s (1-p)^{n_1+n_2-s} \sum_{x_1=a_1+1}^{n_1 \wedge s} \binom{n_1}{x_1} \binom{n_2}{s-x_1} & m = 2, a_1 + 1 \leq s \leq n_1 + n_2 \end{cases}$$

Exact confidence intervals of the UMVUE are obtained as follows:

$$\Pr(\tilde{p}(M, S) \geq \tilde{p}(m, s) | p = p_L) = \alpha/2$$

and

$$\Pr(\tilde{p}(M, S) \geq \tilde{p}(m, s) | p = p_U) = 1 - \alpha/2$$

The transition from Stage 1 to Stage 2 in phase II study will be based on the response rate in the phase II stage 1 patients in FAS. The response rate will be calculated for the final analysis in patients with phase II.

Update: since a no-go decision has been made and Phase II Stage 2 was not started, the UMVUE estimator of p would be equivalent to the simple proportion $\frac{s}{n_1}$.

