7.2.1.2 Measurement of spleen volume by MRI/CT

Patients enrolled to the confirmatory MTD level(s) in the Phase Ib part and all patients enrolled in the Phase II part of the study will have MRI/CT of the abdomen performed at Week 1 Day 1, Week 13 Day 1, the end of Week 24, the end of Week 48, and at Week 105 Day 1. Patients in the extension phase will undergo MRI/CT of the abdomen every 24 weeks from Week 105. All patients will undergo MRI/CT of the abdomen at the End of Treatment visit. Patients who have a $\geq 35\%$ spleen volume reduction at the end of Week 24 and Week 48 compared to Week 1 Day 1 will be considered responders, otherwise they will be considered non-responders. See [Table 7-3](#) for the imaging collection plan.

Table 7-3 Spleen volumetric imaging (MRI/CT) collection plan

| Procedure | Collection time points |
|--|--|
| Abdominal MRI of the spleen (or CT if MRI not permitted) Phase Ib- Patients enrolled to the confirmatory MTD level(s) Phase II- All Patients | Week 1 Day 1 |
| | Week 13 Day 1 |
| | At the end of Week 24 and the end of Week 48, and Week 105 Day 1 |
| | Every 24 weeks from Week 105 for patients in the extension phase |
| | End of Treatment |
| Central Reader: MRI/CT scans will be sent to a central lab for analysis | |

MRIs will be performed locally according to the guidelines provided by the designated imaging vendor. The scans from an individual patient will be sent to the designated imaging vendor, who will then provide an independent quantitative assessment of the spleen volume for the study. Spleen volume will be obtained by outlining the circumference of the organ and determining the volume using a validated technique. The MRI will not determine spleen length below the left costal margin, as there are no validated approaches for determining this

measurement. Specific image acquisition parameters and procedures will be provided by the designated imaging vendor.

MRI is the preferred method for obtaining spleen volume data. However, CT scans may be performed if MRI cannot be performed (because of the presence of metal clips in the body, or because of claustrophobia, for example), or if MRI is unavailable to the study site. CT scans will be similarly processed by the designated imaging vendor.

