10.4.1 Variable

Phase Ib:

The primary variable is the frequency of DLTs associated with continuous daily administration of LDE225 in combination with INC424 as a function of dose. Estimation of the MTD of the combination treatment will be based upon the estimation of the probability of DLT at each dose level using BLRM and guided by EWOC ([Section 10.4.2](#)).

Phase II:

The primary endpoint is the proportion of subjects achieving $\geq 35\%$ reduction in spleen volume from baseline by centrally reviewed MRI/CT at the end of Week 24 and Week 48.

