10.7 Interim analysis

There will be an interim analysis for both safety and efficacy after 18 patients are enrolled in the phase II study. After the first 18 patients are enrolled and observed over a minimum of 24 weeks or until death, documented disease progression, intolerable toxicity, withdrawal of consent, discontinuation at the discretion of the investigator or lost to follow-up, whichever comes first, further enrollment can be stopped for futility if there are less than 8 responders (i.e., spleen volumetric reduction of at least 35% through MRI/CT). This corresponds to a decision threshold of >20% (Bayesian) predictive probability of success to continue enrollment (Table 10-6).

Review of safety data will include, but is not limited to, assessment of the nature and frequency of deaths during treatment, serious adverse events, Grade 3 or 4 adverse events, key laboratory abnormalities, abnormal results from electrocardiogram (ECG) assessments and distribution of safety-related reasons for discontinuation. The trial might be terminated at the interim if treatment is not well tolerated as determined by steering committee (Grade 3-4 AEs >20% may result in termination).

It is possible to terminate the trial at the interim for lack of adequate efficacy, i.e. futility. Assessment of futility will be based on the calculated Bayesian predictive probabilities for the occurrence of the response rate in the FAS.

The efficacy outcome (response rate) is assumed to be binary, namely, response (achieving \geq 35% reduction of spleen volume from baseline by centralized reviewed MRI/CT, Yes vs. No), and the number of responders follow a binomial distribution.

Suppose the prior belief regarding the probability of response (π) is that it has a beta distribution with parameters α_0 and β_0 . If there are x responders out of n patients, then the posterior distribution for π is beta distribution with parameters $\alpha_1 = \alpha_0 + x$ and $\beta_1 = \beta_0 + n - x$. Now let Y represent the number of success from m future observations, then the posterior predictive distribution of Y conditional on the observed data at the interim (x responders out of n patients) is a betabinomial distribution described by

$$p(Y = y|x, n) = \binom{m}{y} \frac{B(\alpha_0 + x + y, \beta_0 + n - x + m - y)}{B(\alpha_0 + x, \beta_0 + n - x)}$$

Where $B(a,b)$ is the beta distribution with parameter a and b .

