1.2 Primary Objectives

The primary objective of Phase Ib is to establish the MTD and/or RPIID of the combination of LDE225 (QD) and INC424 (BID) when administered orally to patients with myelofibrosis who have not previously received therapy with a JAK inhibitor.

The primary objective of Phase II is to assess the efficacy of the co-administration of LDE225 and INC424 on spleen volume reduction as determined by centrally reviewed MRI/CT.

[figure not shown]

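### SAP 3.5.2.1 bases the Phase II primary analysis on the investigator's assessment, although the endpoint is defined everywhere else by centrally reviewed MRI/CT spleen volume

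*SAP*

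**What the plan says.** **SAP 3.5.2.1.** The endpoint is the proportion of patients with at least 35% "reduction in spleen volume from baseline by centrally reviewed MRI/CT at the end of week 24 and week 48". A responder needs evaluable baseline and follow-up volumes, no earlier protocol-defined progression, and a calculated percent change of -35% or less.

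The section then turns to data sources. Response as assessed by the investigator is listed. Of the calculated version it says: "Recalculated response based on raw measurements will be listed additionally and discrepancies will be identified". The next sentence concludes that the investigator's "assessment is considered to be validated and will be used for the primary efficacy analysis".

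**Other definitions of the same quantity:**
- SAP 1.2, Phase II objective: "spleen volume reduction as determined by centrally reviewed MRI/CT". Protocol 10.4 words its objective the same way.
- Protocol 10.4.1, primary variable: "reduction in spleen volume from baseline by centrally reviewed MRI/CT at the end of Week 24 and Week 48".
- Protocol 10.7, response at the interim: "reduction of spleen volume from baseline by centralized reviewed MRI/CT".
- Protocol 7.2.1.2: scans go to the designated imaging vendor, "who will then provide an independent quantitative assessment of the spleen volume for the study". Table 7-3 adds that "MRI/CT scans will be sent to a central lab for analysis".
- Protocol 9.4: imaging is processed centrally and the results are transferred electronically to the sponsor or its CRO.

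**The investigator's role.** The protocol summary leaves patient management with the local investigator. The site-measured spleen response in Protocol 7.2.1.1 is palpable length in Phase Ib, which is a different measure.

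**The concern.** One section names two sources for one endpoint and gives the analysis to the source that the endpoint definition does not mention. If the two disagree for a patient, the SAP has the disagreement identified but gives no rule for resolving it. As written, the investigator's call enters the analysis.

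The trial is open-label with no control arm. A volume measured by an independent vendor is therefore the main guard against an assessor's knowledge of treatment influencing the result. A proportion built on local calls would not answer an objective stated in terms of central review.

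What is at stake is the reported Week 24 and Week 48 response proportions and their confidence intervals.

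**Working it through.** **1. The design figures do not depend on this wording.** Inputs from Protocol 10.7 and 10.8: 18 patients in Stage 1, continue with at least 8 responders, 28 more in Stage 2, success at 23 or more of 46. The exact two-stage probability is

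P(success | p) = Σ over x = 8 to 18 of P(X₁ = x; 18, p) × P(X₂ ≥ 23 − x; 28, p).

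It gives 0.0952 at p = 0.40 and 0.9004 at p = 0.60. These match the stated 9.5% and 90%, and all ten rows of Table 10-7 are reproduced. Confirming the central read as the source changes none of them.

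**2. The passages side by side.**

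| Place | Source of response |
|---|---|
| SAP 1.2, objective | central review |
| SAP 3.5.2.1, endpoint | central review |
| SAP 3.5.2.1, responder rule | calculated volume change ≤ -35% |
| SAP 3.5.2.1, data for the primary analysis | investigator's assessment |
| Protocol 10.4 and 10.4.1 | central review |
| Protocol 10.7 | central review |
| Protocol 7.2.1.2 | vendor's independent volume |

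One row is out of line, and it is the row a programmer would follow. The visible documents do not show whether an investigator volume read exists. The SAP refers some details to RAP M7.1, which was not available.

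**3. Size per discordant patient.** Stage 1 enrolled 20 (SAP 3.5.2.1.2), so one patient is 100/20 = 5.0 points. The pooled Phase Ib expansion plus Stage 1 group (SAP 1.6 and 3.5.2.1.3) has 7 + 20 = 27, so one patient is 100/27 = 3.7 points.

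Observed counts are not in the documents. The following are illustrations with Clopper-Pearson 95% limits:
- 7/20 = 35.0% (15.4 to 59.2)
- 8/20 = 40.0% (19.1 to 63.9)
- 9/20 = 45.0% (23.1 to 68.5)
- 11/27 = 40.7% (22.4 to 61.2)
- 12/27 = 44.4% (25.5 to 64.7)

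The counts 9/20 and 12/27 are also the go thresholds in SAP 3.5.2.1.2 and 3.5.2.1.3. With the Beta(1,1) prior and 26 further patients, the beta-binomial predictive probability is 0.149 for 8/20 and 0.325 for 9/20, as the SAP table shows. The 20% criterion lies between them, so at that point one reclassified patient would change the rule's answer.

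**4. Secondary point: the denominator.**
- SAP 3.5.2.1 makes an evaluable baseline a condition of being a responder and defines n₁ as patients accrued. It bases the Stage 1 transition on the FAS. A patient without a baseline scan then counts as a non-responder.
- SAP 3.5.3 makes a baseline volume a condition for inclusion in the primary efficacy analysis, so the same patient is excluded. It also counts unknown response as non-response.

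If one patient lacked a baseline scan (an assumption; none is documented), 8 responders would be 8/20 = 40.0% or 8/19 = 42.1% (20.3 to 66.5). In the pooled group, 11 responders would be 11/27 = 40.7% or 11/26 = 42.3% (23.4 to 63.1).

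**The case against.** **The sentence may have nothing to act on.** If only the vendor measures volume, the sentence is an editorial slip, possibly template text. The investigator's assessment might also be a responder status recorded at the site from the vendor's volumes, with the recalculation as an arithmetic check. That would fit the word validated. A footnote to Protocol Table 7-5 shows that a Week 24 responder status is used during conduct, though not who assigns it. These readings are possible, but none is in the text, and each would need the same rewording.

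**Central handling may mean only collection and quality control**, as the protocol summary and Protocol 9.3 could suggest. Protocol 7.2.1.2 goes further and assigns the volume measurement to the vendor.

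**No bias is shown.** This stands. No discordant patient is documented, and discrepancies would at least be visible in the listings.

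**The no-go decision is already made.** Rewording cannot undo it, and the SAP attributes it to the Steering Committee's recommendation and an internal decision. However, the documents do not say which source fed the interim count.

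**The intervals above are not the SAP's own.** This also stands. For 8/20 with a stop at Stage 1, the SAP's printed upper-limit equation reduces to P(X ≥ 8 | 20, p) = 0.975. That is the Clopper-Pearson upper limit for 7/20, 59.2%, rather than 63.9%. The lower limit agrees at 19.1%. The size per patient is unaffected.

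**The 27-patient calculation is labelled exploratory, and SAP 3.5.3 can be read coherently on its own.** Both are fair. The group of 27 is nevertheless one of the SAP 1.6 reporting groups, and SAP 3.5.3 still does not agree with the accrued-patient and FAS wording in 3.5.2.1.

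**Conclusion.** The concern holds. SAP 3.5.2.1 contradicts its own endpoint, the SAP objective and the protocol on which data determine the primary response, and no visible passage resolves it. Confidence is high for the conflict in the text; no effect on results is claimed.

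The possible effect is 5.0 points per discordant patient at n = 20 and 3.7 points at n = 27, confined to the reported response proportions and their intervals. The number of discordant patients is unknown and may be zero.

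The denominator inconsistency is real but minor. It matters only if a treated patient lacks a baseline scan. This should be fixed before the response rates are reported.

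**What to change.** Replace the sentence in SAP 3.5.2.1 with wording such as: *Response will be derived from the central imaging vendor's spleen volumes, and this derived response is used for the primary analysis; any investigator-recorded response is listed only.* State that raw measurements means the vendor's volumes. It would also help to record which source was used for the interim count.

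In the same edit, state one denominator, preferably all treated Stage 1 patients in the FAS with a missing baseline counted as non-response. If the baseline requirement in SAP 3.5.3 is kept, align 3.5.2.1 with it and report how many patients are excluded.

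The cost is SAP wording only. The central volumes are already collected, and no new data or design change is needed.

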After declaration of MTD and/or RPIID, the dose will be expanded by an additional 6 patients in order to further assess tolerability, safety and early efficacy. If two MTDs/RPIIDs are established, each MTD/RPIID will enroll an additional 6 patients in the safety expansion. After these confirmatory patients have been treated for 6 weeks, if 2 or more DLTs are observed at the selected dose (MTD/RPIID), the BLRM will be ran again to confirm that the current dose still satisfies the overdose criteria of the model. If the dose fails to satisfy the criteria, a change to the dose under study will be made subject to the BLRM recommendation.

Listing of DLTs

DLTs will be listed and their incidence summarized by primary system organ class, worst grade based on the CTCAE version 4.03, type of adverse event, and by dose cohort. The dose-determining set will be used for these summaries.

Phase II:

In the final analysis, the uniformly minimum variance unbiased estimator (UMVUE; [Jung 2004](#)) for the proportion of subjects achieving $\geq 35\%$ reduction from baseline in spleen volume as measured by MRI/CT at the end of Week 24 weeks Week 48, and their exact two-sided 95% confidence intervals will be provided. Patients with unknown response will be treated as non-responders (see [Section 10.4.3](#)).

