The prior for the response rate is assumed to follow a Beta(1,1) distribution, which corresponds to a priori expectation of 50%. If there are 8 or more responders, after the first 18 patients have been observed for 24 weeks, then 28 additional patients will be enrolled into stage 2. Encouraging efficacy will be concluded if the observed ORR exceeds 50% (i.e. 23/46) at the end of Phase II.

In this study, futility is equivalent to observe less than 8 responders in 18 patients (Table 10-6). However, the cut-off for the number of responders needed will be determined at the time of interim analysis based on the actual number of patients enrolled in the study following the algorithm defined in the protocol.

Table 10-6 Predictive probability of observing response rate of 50% (n=18) or greater in the FAS at the primary analysis (46 patients) under different interim results

| Observed response at IA | | Predictive probability of observing response rate $\geq 50\%$ |
|-------------------------|------|---|
| # of response | % | |
| 4 | 22.2 | 0.002 |
| 5 | 27.8 | 0.011 |
| 6 | 33.3 | 0.047 |
| 7 | 38.9 | 0.143 |
| 8 | 44.4 | 0.318 |
| 9 | 50.0 | 0.548 |
| 10 | 55.6 | 0.762 |
| 11 | 61.1 | 0.905 |
| 12 | 66.7 | 0.972 |
| 13 | 72.2 | 0.994 |

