1.1 Study design

[figure not shown]
This study consists of an open-label, multi-center, dose-finding phase Ib including dose escalation and expansion followed by a phase II in patients with MF.

The study has 3 parts:

- (1) Screening: 21 days screening assessment period prior to receiving the first study treatment.
- (2) Treatment: it includes the dose escalation and dose expansion in phase Ib and stage 1 and stage 2 in phase II. The stage 2 enrollment in phase II depends on the result for the interim analysis (IA). The treatment period is from Day 1 for up to 2 years or until death, documented disease progression, initiation of a new MF therapy, intolerable toxicity, withdrawal of consent, discontinuation at the discretion of the investigator, lost to follow-up or premature termination of the study, whichever comes first. Based on the recommendation from SC and internal decision, there will be no enrollment to Phase II Stage 2.
- (3) Follow up: 30 days following up after the last day of treatment.

The flow chart of the study design is in [Figure 1-1](#).

Figure 1-1 Study design of CLDE225X2116

Note: Patients who complete 2 years of treatment and are deriving clinical benefit in the opinion of the investigator will be allowed to continue receiving treatment (LDE225 and INC424) in an extension phase of this study, until discontinuation reasons are met or an alternative setting to receive study treatment (e.g., in form of another protocol) becomes available.

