3.7 Exploratory analysis

3.7.2 Spleen length by manual palpation

Frequency of patients who have palpable spleen measurement will be provided. Spleen measurement by manual palpation at week 24 will be compared to the week 1 day 1 measurement. Descriptive statistics will be provided for the spleen length and percent change from baseline over time by the redefined treatment groups (details can be found in RAP M7.1 section 1.2.1) and overall. The maximum likelihood estimate and 95% exact binomial confidence interval will be also provided for patient who has $\geq 50\%$ spleen length reduction by manual palpation.

Data will be summarized for the set of patients from the FAS who have a valid corresponding baseline assessment.

The percentage change in spleen length is defined as:

$\% \text{ Change} = (\text{Post-baseline spleen length} - \text{Baseline spleen length}) \times 100 / \text{Baseline spleen length}$.

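### The SAP's upper-limit equation for the Phase II exact 95% confidence interval leaves the observed result out of the tail, so the limit is too low

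*SAP*

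**What the plan says.** Protocol 10.4.2 plans the UMVUE of the proportion of patients with at least a 35% spleen volume reduction, "and their exact two-sided 95% confidence intervals will be provided". SAP 3.5.2.1 repeats this, "with the exact two-sided 95% confidence interval will be provided in phase II", and then gives the construction: "Exact confidence intervals of the UMVUE are obtained as follows". Writing p̃ for the UMVUE, the two equations are:

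- lower limit: Pr(p̃(M,S) ≥ p̃(m,s) | p_L) = α/2
- upper limit: Pr(p̃(M,S) ≥ p̃(m,s) | p_U) = 1 − α/2

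The relation sign is the same in both.

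The Update at the end of that section says that, "since a no-go decision has been made and Phase II Stage 2 was not started", the UMVUE reduces to s/n1. It does not mention the interval. SAP 1.1 gives the reason for closing Stage 2: "Based on the recommendation from SC and internal decision, there will be no enrollment to Phase II Stage 2". For palpated spleen length, SAP 3.7.2 plans a standard interval: "The maximum likelihood estimate and 95% exact binomial confidence interval will be also provided".

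**The concern.** The number of responders is discrete, so the sign matters. The complement of Pr(p̃ ≥ observed) = 1 − α/2 is Pr(p̃ < observed) = α/2, and that tail omits the observed outcome. An exact upper limit needs Pr(p̃ ≤ observed | p_U) = α/2. As printed, the limit belongs to the next lower outcome.

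This is the planned interval for the Phase II primary endpoint. Followed literally, it would be labelled exact 95% without having that property, and it would make low response rates look better established than they are. The same count in 20 patients would also get a lower upper limit here than under the exact binomial method planned for spleen length.

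A related gap concerns the printed probability function, which covers a Stage 1 stop only for s up to the futility boundary a1. Stage 2 was closed on a committee recommendation and an internal decision, and the documents do not give s. If s was above a1, the SAP defines no interval.

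**Working it through.** **Inputs.** α = 0.05 (Protocol 10.4.2, SAP 3.5.2.1). Actual Stage 1: n1 = 20, go at 9 or more responders, so a1 = 8, with n2 = 26 (SAP 3.5.2.1.2). Planned design: n1 = 18, a1 = 7, n2 = 28 (Protocol 10.7). Reference rates: 40% as no benefit and 60% as the power alternative (Protocol 10.8), and the 50% success mark (Protocol 10.7).

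**The plan's own figures first.** Going on at 8/18 or more and succeeding at 23/46 or more gives 0.0952 at a true rate of 40% and 0.9004 at 60%, matching the stated 9.5% and 90%. Beta(1,1) predictive probabilities reproduce every row of the SAP's 20-patient table (for example 0.149 at 8 and 0.325 at 9). The design inputs are therefore read correctly.

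**Limits after a Stage 1 stop, n1 = 20.** For s ≤ 8 the estimate is s/20 and the ordering of outcomes is strictly increasing, so the equations become binomial:

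- printed: Pr(X ≤ s − 1 | p_U) = 0.025
- exact: Pr(X ≤ s | p_U) = 0.025

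The printed limit for s is thus the Clopper-Pearson limit for s − 1.

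| s | lower limit | printed upper | exact upper | Pr(X ≤ s) at printed upper |
|---|---|---|---|---|
| 0 | 0 | no solution | 0.168 | – |
| 4 | 0.057 | 0.379 | 0.437 | 7.4% |
| 5 | 0.087 | 0.437 | 0.491 | 7.0% |
| 6 | 0.119 | 0.491 | 0.543 | 6.8% |
| 7 | 0.154 | 0.543 | 0.592 | 6.6% |
| 8 | 0.191 | 0.592 | 0.639 | 6.5% |

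The last column should be 2.5%. At s = 0 the event has probability 1 for every p, so the printed equation cannot be solved. Applied to a single stage, 20/20 gets an upper limit of 0.9987, below its own estimate of 1.

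**Reading against the protocol's rates.** A rate is excluded from above when the tail probability is below 2.5%:

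- 4/20 against 40%: Pr(X ≤ 3) = 1.6% as printed; Pr(X ≤ 4) = 5.1% exact.
- 6/20 against 50%: Pr(X ≤ 5) = 2.1% as printed; Pr(X ≤ 6) = 5.8% exact.
- 8/20 against 60%: Pr(X ≤ 7) = 2.1% as printed; Pr(X ≤ 8) = 5.7% exact.

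In each case the printed interval excludes the rate and the exact interval does not.

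**Coverage.** All outcomes were enumerated with the SAP's probability function, ordered by the UMVUE, and summed at 501 values of p from 0.200 to 0.700.

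| design | printed coverage | mean | share of p below 95% | corrected minimum | largest upper-side miss, printed |
|---|---|---|---|---|---|
| single stage, 20 | 89.4%–96.9% | 93.9% | 69% | 95.8% | 9.3% |
| 20 + 26 | 88.5%–96.3% | 93.8% | 79% | 95.1% | 9.3% |
| 18 + 28 | 88.5%–96.3% | 93.5% | 72.5% | 95.3% | 9.9% |

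Over this range the printed upper-side miss rate is never below 2.5%. Once corrected, it is never above 2.5%. The corrected 20 + 26 limits for s = 0 to 8 equal Clopper-Pearson.

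**The case against.** The intent is plain: both documents promise an exact 95% interval, the SAP lists the Clopper-Pearson paper among its references, and with a single stage and estimator s/n1 a standard routine would return the right limits. Harm arises only if someone codes the printed line. That is fair, but such output would depart from the written SAP, and the Update does not replace the interval equations.

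The finding rests on one relation sign in text extracted from a PDF. The formulas around it read cleanly, but the sign should be checked.

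No decision depends on the interval. The protocol judges success on the observed rate: "Encouraging efficacy will be concluded if the observed ORR exceeds 50"%. This stands. The comparison with 40%, 50% and 60% is a reader's use of the protocol's rates, not one of its rules.

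The lowest coverage occurs at low true rates (p = 0.249 for n = 20). At 40%, 50% and 60%, printed coverage at n = 20 is 92.8%, 92.2% and 92.8%, which is milder but still short. The error would also have been small after Stage 2: 23/46 in the 20 + 26 design gives 0.654 against 0.665. Stage 2 was not run, and the error is largest for a Stage 1 stop.

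Spleen length is a different endpoint, so the contrast with SAP 3.7.2 concerns method only. SAP 3.5.3 requires a baseline spleen volume, so the denominator could fall below 20. Neither point changes the equation.

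**Conclusion.** The concern holds. As printed, the upper limit is not exact and 95% coverage is not guaranteed; the lower limit is correct. At n = 20 the upper limit is 4.7 to 5.8 percentage points too low for s = 4 to 8. Of the nine no-go results under the 20-patient rule (s = 0 to 8), three change their reading against a protocol reference rate (4, 6 and 8 responders), and a fourth (s = 0) has no printed upper limit.

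This assumes that the original PDF shows the same sign and that the analysis uses all 20 enrolled Stage 1 patients. The observed s is not in the documents, so the effect is given as a range. The point should be fixed before the result is reported; it does not bear on the go/no-go decision.

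**What to change.** Check the relation sign in the original PDF. If it is ≥, replace the second equation with Pr(p̃(M,S) ≤ p̃(m,s) | p_U) = α/2, which is the same as changing ≥ to >. State that p_L = 0 at the smallest outcome and p_U = 1 at the largest.

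Add one sentence to the Update: because Stage 2 was not opened, the reported interval is the Clopper-Pearson interval for s/20. For s ≤ 8 this equals the corrected two-stage interval, and it is also defined if s was above the futility boundary.

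The cost is one symbol, the end-point conventions and one sentence. The reported upper limit rises by about 5 points for s = 4 to 8. No design feature or decision rule changes.
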